8.1.4 Storage Conditions

Storage of IMP is according to standard hospital procedures in a key closed cupboard at room temperature and is monitored correctly since November 2020.

8.2 Administration of experimental and control interventions

8.2.1 Experimental Intervention

IV bolus injection of lidocaine 1,5 mg/kg and approximately 30 minutes before incision, followed by a continuous IV infusion of lidocaine of 3,0 mg/kg/h until 2 hours after skin closure. Signs of toxicity (for central nervous system like somnolence, tinnitus, slurred speech, cramps, visual disturbances, seizures and for the heart like negative inotropia, bradycardia, vasodilation) may start to appear at plasma levels of 5 µg/ml. However, it usually takes up to 10 µg/ml of lidocaine plasma levels for these signs to appear. Using the regimen of lidocaine administration of 1,5 mg/kg, IV bolus dose, followed by continuous infusion at 3,0 mg/kg/h, the following plasma concentrations of lidocaine were observed: $1,9 \pm 0,7 \mu\text{g/ml}^{11}$ and $2,1 \pm 0,4 \mu\text{g/ml}^7$, respectively

8.2.2 Control Intervention

Same procedure as in the lidocaine arm, but with blinded placebo solution (NaCl 0,9%)

8.3 Dose / Device modifications

The drug dose is based on the body weight, which was evaluated preoperatively. No dose modifications are provided in the intervention.

8.4 Compliance with study intervention

n/a

8.5 Data Collection and Follow-up for withdrawn participants

Data from patients who are withdrawn from the study due to surgical conversion will not be used in the study. Data from patients who withdraw after the surgery, will anonymized still be used, and the patient will not be replaced.

Lidocaine is a well-known and well-used medication that has been on the market since 1943. It has a short half-life of 2-3 hours. Withdrawn patients or patients who have withdrawn from the study, will still obtain their routine check-ups. There are no follow up visits specifically for the study.

8.6 Trial specific preventive measures

There are no trial specific preventive measures.

8.7 Concomitant Interventions (treatments)

Intraoperative analgesia will be given as deemed necessary by the anaesthesiologist, using fentanyl as well as continuous infusion of remifentanyl. The following rules need to be applied concerning opioid administration: Before surgical incision administration of at least 4 µg/kg of fentanyl IV as bolus, no more than 1 µg/kg of fentanyl per hour IV thereafter; additional analgesia is covered by adjusting remifentanyl infusion; the last dose of fentanyl is administered at least 60min before the end of the surgical procedure. This should minimize the variability of intraoperative opioid administration during the study. No infiltration of local anaesthetics is allowed. At the end of surgery, after haemostasis and if not contraindicated, metamizol 1 g will be given IV.

8.8 Study Drug Accountability

Lidocaine and NaCl are standard medical products at our hospital. They are available in the OR and are in general use and accordingly stored following their SOPs. Batch numbers but no info regarding the medication used, will be archived in the dispensing log.

The Lidocaine/placebo will be prepared after patient inclusion and randomization in syringes marked with patients study number (Patient ID) by the anaesthesiologist or dedicated study nurse of the department that is not participating in surgery (according to the delegation log) just before surgery and storage in a designated cooler until administered. The IMPs data will be recorded in the Drug Accountability Sheet accessible for a potential emergency unblinding. The dedicated investigator or

[figure not shown]
delegate will keep an accurate Drug Accountability Log including the physical location dates (despense to Participant), batch number expiry date, and quantities (prepared, returned,).

8.9 Return or Destruction of Study Drug

Used IMP should be disposed in accordance with local practice following reconciliation and the completion of the relevant log (see 8.8.)

9. STUDY ASSESSMENTS

9.1 Study flow chart(s) / table of study procedures and assessments

9.2 Assessments of outcomes

9.2.1 Assessment of primary outcome

Pain Service Team will instruct the patient in the use of PCA according to hospital standards. PCA will be started (PCA setting: demand dose of 2 mg morphine and a lockout of 12 min; if required, it can be adjusted to patient's need).

Total PCA requests and positive PCA requests, are recorded by the equipment. Pain intensity using the VAS and total morphine consumption in mg will be recorded at timepoints 1 hr, 2 hrs, 4 hrs, 8 hrs, 16 hrs, and 24 hrs after skin closure. The pain score will be documented when the patient is immobile and when the patient is coughing.

9.2.2 Assessment of secondary outcomes

Pain and morphine consumption

Pain intensity using the VAS and total morphine consumption will be recorded 1, 2, 4, 8, 16, 24 and 48 hours after skin closure.

Nausea and vomiting

On arrival in the PACU the patient will be asked if they are nauseous.

The patients will be instructed to inform the staff of any nausea or vomiting that they may experience.

First defecation

Once on ward, the patients will be questioned at timepoints 1 hr, 2 hrs, 4 hrs, 8 hrs, 16 hrs, 24 hrs and 48 hrs after skin closure regarding their bowel movements and the patients will be instructed to inform the staff of their first defecation.

The approximate time of the first defecation will be recorded in the CRF.

Length of hospital stay

Defined as time from surgery until patients are discharged from the hospital

Chronic pain assessment

During follow up at 2 weeks (+2 weeks), 3 and 6 months (± 7 days), patients will be assessed for pain intensity (VAS 1 to 10) while being immobile and while coughing, pain experience (no pain, mild, discomforting, distressing, horrible, excruciating) and for the sensory and affective dimension of pain with the short-form McGill Pain Questionnaire

9.2.3 Assessment of other outcomes of interest

30-day mortality

To be assessed from the patient records. Defined as death within the first 30 days after surgery.

9.2.4 Assessment of safety outcomes

9.2.4.1 Adverse events

n/a

9.2.4.2 Laboratory parameters

n/a

9.2.4.3 Vital signs

Nothing specific to the study. Only routine measurements

9.2.5 Assessments in participants who prematurely stop the study

Patients who have withdrawn from the study or who have been withdrawn will still have their routine surgical follow up at 2 weeks, 3 months and 6 months after the surgery.

9.3 Procedures at each visit

	Screening	OR	Ward							Follow up			
Day	-1 to -7	0	1							2	14(+14)	90 (±7)	180(±7)
Time (hr)		0	1	2	4	8	16	24	48				
Informed consent	X												
Demographics	X												
Medical history	X												
Pregnancy test	X												
In/Exclusion Criteria	X												
Randomisation		X											
Study medication administered		X											
Perioperative data		X											
PCA data			X	X	X	X	X	X	X				
Pain data			X	X	X	X	X	X	X	X	X	X	
Nausea and vomiting			X	X	X	X	X	X	X				

9.3.1 Screening visit (Day -1 to -7)

Study explained to patient

Informed consent obtained

Patients are screened for eligibility

Pregnancy of females in reproductive age:

Before study inclusion a serum beta HCG test is required if a pregnancy can not be definite excluded otherwise (e.g. hysterectomy, ≥ 45 years of age and has not had menses for greater than 1 year). Serum beta HCG test is valid within 7 days before study inclusion.

9.3.2 Pre-operative day (may be the same day as the screening visit)

The routine procedure is that the patients will be instructed how to use a patient controlled analgesia (PCA) pump, how to rate pain intensity on a visual analog scale (VAS: 0 as “no pain” and 10 as “worst

imaginable pain”) and answer the short-form McGill Pain Questionnaire (pre operation). The following baseline data will be collected:

- Date of Informed Consent signed (day/month/year)
- Gender
- Weight and height
- Inclusion/Exclusion criteria
- Date of admission to the hospital (day/month/year)
- Diagnosis and type of planned surgery
- Operative risk as evaluated according to the American Society of Anaesthesiologists (ASA)

9.3.3 Perioperative (day -1 to day 0)

Randomization by anesthesiologist, delegated study nurse of the department or thoracic surgeon not involved in the patient care or assessment.

Notation of treatment of sequentially numbered patient on drug accountability sheet which is only available for doctor not involved in the care and/or assessment of the patients in the study and on Drug accountability Log for Lidocaine and NaCl

Collection of perioperative data by surgical nurse and study coordinator:

- Surgeon
- Type of surgery
- Date of surgery (day/month/year)
- Duration of Surgery (skin-incision-skin closure) (min)
- Duration of anaesthesia (min)
- Number of trocars
- Intraoperative fentanyl (μg) and Remifentanyl (μg)
- Duration of study medication infusion (min)
- Intraoperative study medication infused (mg) (will be later calculated to avoid unblinding)
- Additional analgesic medication (metamizol,)
- Intraoperative complications

9.3.4 Data of patient-controlled analgesia (PCA)

- Total morphine consumption (mg)
- Total PCA requests
- Positive PCA requests
- Negative PCA requests
- Pain intensity (VAS Score) – with coughing and when immobile
- Riker sedation agitation scale¹⁸PONV [nausea, present or not; vomiting, number of events]
- Adverse events of lidocaine infusion (light headedness, drowsiness, perioral numbness, visual disturbances, metal taste)
- Additional analgesic medication including dose and time of intake during the hospital stay

9.3.5 Hospital stay and follow up data (postoperative day 1 and 2, follow up 2-4 weeks, 3 and 6 months later)

Daily ward rounds until discharge by the surgeon and his delegates to assess the patient for complications. Follow up is performed by the surgeon and the study coordinator during the visit at our outpatient clinic or per telephone inquiry

- Date of discharge from the hospital (day/month/year)
- Pain intensity [VAS Score] – with coughing and when immobile
- Additional analgesic medication including dose and time/date of intake during the hospital stay

10. SAFETY

10.1 Drug studies

During the entire duration of the study, all serious adverse events (SAEs) are collected, fully investigated and documented in source documents and case report forms (CRF). Study duration encompassed the time from when the participant signs the informed consent until the last protocol-specific procedure has

been completed, including a safety follow-up period.

10.1.1 Definition and assessment of (serious) adverse events and other safety related events

n/a

A **Serious Adverse Event (SAE)** is classified as any untoward medical occurrence other than those listed, that:

- results in death,
- is life-threatening,
- requires in-patient hospitalization or prolongation of existing hospitalisation,
- results in persistent or significant disability/incapacity, or
- is a congenital anomaly/birth defect.

In addition, important medical events that may not be immediately life-threatening or result in death, or require hospitalisation, but may jeopardise the patient or may require intervention to prevent one of the other outcomes listed above should also usually be considered serious. [ICH E2A]

SAEs should be followed until resolution or stabilisation. Participants with ongoing SAEs at study termination (including safety visit) will be further followed up until recovery or until stabilisation of the disease after termination.

Assessment of Causality

Both Investigator and Sponsor-investigator make a causality assessment of the event to the study drug, based on the criteria listed in the ICH E2A guidelines:

Relationship	Description
Definitely	Temporal relationship Improvement after dechallenge* Recurrence after rechallenge (or other proof of drug cause)
Probably	Temporal relationship Improvement after dechallenge No other cause evident
Possibly	Temporal relationship Other cause possible
Unlikely	Any assessable reaction that does not fulfil the above conditions
Not related	Causal relationship can be ruled out
*Improvement after dechallenge only taken into consideration, if applicable to reaction	

Unexpected Adverse Drug Reaction

An "unexpected" adverse drug reaction is an adverse reaction, the nature or severity of which is not consistent with the applicable product information (e.g. Investigator's Brochure for drugs that are not yet approved and Product Information for approved drugs, respectively). [ICH E2A]

Suspected Unexpected Serious Adverse Reactions (SUSARs)

The Sponsor-Investigator evaluates any SAE that has been reported regarding seriousness, causality and expectedness. If the event is related to the investigational product and is both serious and unexpected, it is classified as a SUSAR.

This is a double-blinded study. In case unblinding is needed in order to determine SUSAR, the treatment allocation should not be disclosed to the investigator, nor to the study staff, in order not to make the subject ineligible.

Assessment of Severity

The SAE terms will be reported according to the Common Terminology Criteria for Adverse Events

(CTCAE, Version 4.0).

10.1.2 Reporting of serious adverse events (SAE) and other safety related events

Reporting of SAEs

Underlying disease (e. g. metastatic lung cancer with expected 1 year survival of 27-37%) is an acute or chronic comorbidity or condition designated as one of the principal diagnosis not related to the procedure that alters short and/or long term survival of the patient.

All SAEs, except those related to the underlying disease of the patient, must be reported immediately and within a maximum of 24 hours to the Sponsor-Investigator of the study. The Sponsor-Investigator will re-evaluate the SAE form and return the form to the site.

SAEs resulting in death, except those related to the underlying disease of the patient, are reported to the Ethics Committee via BASEC within 7 days.

Reporting of SUSARs

A SUSAR needs to be reported to the Ethics Committee (local event via local Investigator) via BASEC and to Swissmedic (via Sponsor-Investigator) within 7 days, if the event is fatal, or within 15 days (all other events).

Reporting of Safety Signals

All suspected new risks and relevant new aspects of known adverse reactions that require safety-related measures, i.e. so-called safety signals, must be reported to the Sponsor-Investigator within 24 hours. The Sponsor-Investigator must report the safety signals within 7 days to the local Ethics Committee (local event via local Investigator) and to Swissmedic.

Periodic reporting of safety

An annual safety report is submitted once a year to the local Ethics Committee via local Investigator and to Swissmedic via Sponsor-Investigator.

10.1.3 Follow up of (Serious) Adverse Events

Participants terminating the study (either regularly or prematurely) with

- reported ongoing SAE

will return for a follow-up investigation. This visit will take place up to 30 days after terminating the treatment period. Follow-up information on the outcome will be recorded on the respective AE page in the CRF. All other information has to be documented in the source documents. Source data has to be available upon request.

In case of participants lost to follow-up, efforts should be made and documented to contact the participant to encourage him/her to continue study participation as scheduled. In case of minor AEs a telephone call to the participants may be acceptable.

All new SAE that the investigators will be notified of within 30 days after discontinuation of study medication have to be reported in appropriate report forms and in the CRF if required.

Follow-up investigations may also be necessary according to the investigator's medical judgment even if the participant has no AE at the end of the study. However, information related to these investigations does not have to be documented in the CRF but must be noted in the source documents.

11. STATISTICAL METHODS

Detailed methodology for summaries and statistical analyses of the data collected in this study will be documented in a statistical analysis plan. The statistical analysis plan will be finalized before database closure and will be under version control at the Clinical Trial Unit, University Hospital Basel.

11.1 Hypothesis

H₀: Patients treated with lidocaine suffer the same integrated pain expression (as quantified using the SIA score) as patients in the placebo arm.

H₁: Patients treated with lidocaine suffer less integrated pain expression (as quantified using the SIA score) as patients in the placebo arm.

The SIA score integrates total morphine consumption and pain quantified using a VAS. It will be calculated as described in Dai *et al.*(2013)¹⁴ involving all three steps described in the paper.

11.2 Original Sample Size estimation

The original sample size was determined using simulations based on two sources of information:

- The results reported in a similar Study (Dai *et al.*¹⁴ 2013) were used to make an informed assumption about the variability of pain intensity as well as the correlation between experienced pain and the amount of morphine taken.
- The variability in morphine consumption was estimated based on pilot data from patients treated in Basel.

The original estimate of 56 patients was based on the following assumptions:

- Standard deviation of pain: 1.91
- Standard deviation of morphine dose: 1.60 (not log transformed)
- Correlation between pain and morphine: 0.22

The sample size was calculated to achieve an 80% power to find a SIA difference associated with a pain reduction of 1.5 points on the visual analogue scale and a reduction of morphine consumption of 2 mg.

11.3 Interim analysis to update sample size estimation

As planned in the study protocol, we updated our sample size estimate based on the data when at least 10 evaluable patients per arm are recruited. Specifically, the sample size re-estimation was performed when a total of 34 were recruited with 15 patients in the smallest treatment arm. Note that this sample size re-estimation was performed on the data that is not used for the final analysis, for reasons discussed above concerning the layering temperature of the lidocaine. We strongly believe that the information used for this sample size re-estimation - the variability of the outcome in the treatment arms - is not meaningfully influenced by the fact that in the lidocaine arm, the medicament temperature was not monitored correctly. Therefore, we deem the estimate of the variability generalizable to the new data which is collected now monitoring is assured.

We resampled data from the first 34 patients. Note that in the resampling procedure, the pain and morphine value of each patient were kept together as a pair, so that the correlation between both variables was kept intact.

Note that the statistician performing this analysis was blind to the treatment arm labels during the analyses. For both pain and morphine, the arm-means were subtracted from each value. This has two advantages: 1) If we would simply resample the raw values across arms, our simulation would be

based on too large a variance if there truly were a difference between the treatment arms. 2) The subtraction of the arm means assures that the data analyst is really blind to eventual effects in the data while performing the sample size re-estimation.

The result of the resampling analysis is shown in Figure 1. The figure shows the total number of evaluable patients (both arms together, on the y-axis) required to reach different levels of power (separate lines), given a range of true effect sizes in terms of θ (x-axis). The Figure is based on samples with replacement from the interim data set, where in each simulation, the treatment effect on morphine use was set to θ and the effect on pain to $0.75 \cdot \theta$.

We can see that, based on the data collected up to this sample size re-estimation, the required sample size has changed: The original estimation suggested that a total of 56 evaluable patients sufficed to achieve an 80% power of detect a difference as large as $\theta = 2$ (where the treatment effect on morphine intake is of size θ and the effect on pain is of size 0.75 times θ). The updated analysis suggests that 42 evaluable patients are needed, i.e., 21 per treatment arm. To achieve this number of evaluable patients, and given the updated drop-out rate of 30 %, 59 patients should be recruited.

To reach a power of 90%, data of 79 participants is needed, in order to have 55 evaluable patients, given the updated drop-out rate of 30 %.

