
Study Product / Intervention:
	
Lidocaine arm: Intravenous [IV bolus] injection of lidocaine 1,5 mg/kg before intubation and at least 30 minutes before incision, followed by a continuous IV infusion of lidocaine 3,0 mg/kg/h, until 2 hours after skin closure. The patient can be transferred to the ward after the PACU discharge criteria are met. PACU discharge criteria are standardized for the University Hospital Basel.

Control Intervention (if applicable):
	
Placebo arm: Likewise procedure as in the lidocaine arm, but with placebo solution (NaCl 0,9%).

Number of Participants with Rationale:
	
113
 
For this study, 113 patients should be recruited to ensure 42 evaluable patients, assuming a drop-out rate of 25 %. This sample size allows with a power of 0.8 to show a group difference in the SIA score assuming a daily reduction in morphine consumption due to lidocaine of 2 mg and a reduction in the pain score of 1.5 points.
 
We have to expand the 59 to 113 patients since we intend to include in our final statistical analysis only patients who are treated with lidocaine stored as described in the product information. The storage temperature is correctly monitored since November 2020.

Study Duration:
	
The study should take about 4 years to be completed.

[figure not shown]
Study Schedule:	First-Participant-In: April 2019 Last-Participant-Out: anticipated December 2022

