11.5 Planned Analyses

11.5.1 Primary Analysis

The primary endpoint of this study is the SIA score as described in Dai et al.¹⁴. The SIA score integrates total morphine consumption in mg within the first 24 hours post surgery and Pain (VAS) in the first 24 hours after surgery. Pain is assessed several times. The average of all measurements taken in a patient will be used to calculate the SIA score.

The SIA score will be analyzed in a linear model. Treatment arm will be included as two-level factor ("lidocaine" vs "placebo"). Duration of surgery and number of trocars will be included as covariates.

Model validation will be performed by checking residuals and leverages. The residuals will be checked by visual inspection using a plot of the residuals vs the fitted values and a Normal Q-Q plot. In case of substantial violations of model assumptions, transformations or the use of a generalized linear model will be considered. The estimated treatment effect, the 95% confidence interval thereof and the p-value will be presented. The analysis will be performed using $\alpha=0.05$ (two-sided).

The analysis will be performed on the ITT set.

A sensitivity analysis will be performed on the PP analysis set and compared to the main analysis in order to investigate the influence of protocol deviations.

[figure not shown]

Figure 1: The total number of evaluable patients (both arms together, on the y-axis) required to reach different levels of power (separate lines), given a range of true effect sizes in terms of theta (x-axis). The figure is based on simulations, where in each simulation, the treatment effect on morphine use was set to theta and the effect on pain to $0.75 \cdot \theta$.

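### As described, the sample size re-estimation resamples arm-mean-centred values with no degrees-of-freedom correction, so 42 and 55 evaluable patients are mildly optimistic on average

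*Protocol*

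**What the plan says.** Protocol section 11.3 describes a re-estimation done when 34 patients had been recruited, 15 of them in the smaller arm, so 15 and 19. Each patient's pain and morphine values are kept as a pair. Then "For both pain and morphine, the arm-means were subtracted from each value". The section gives two reasons for this: pooling raw values across arms would inflate the variance if the treatment works, and centring keeps the analyst blind to any effect. Power is read from "samples with replacement from the interim data set", where "the treatment effect on morphine use was set to θ and the effect on pain to" 0.75 times θ.

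The results are "The updated analysis suggests that 42 evaluable patients are needed, i.e., 21 per treatment arm" for 80% power at θ = 2, and for the higher target "To reach a power of 90%, data of 79 participants is needed, in order to have 55 evaluable patients". The synopsis repeats the first result: "This sample size allows with a power of 0.8 to show a group difference in the SIA score". Section 11.5.1 sets a two-sided 5% test.

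Section 11.3 does not say whether the centred values were rescaled before resampling.

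**The concern.** Centring is sound and should stay. It has a side effect, though: values centred on means estimated from the same data lie closer to those means than to the true ones. Their spread, taken with divisor n, understates the true variance unless the lost degrees of freedom are restored. Section 11.3 guards against a variance that is too large but does not mention the downward bias that its own remedy introduces.

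Variability is the one quantity this exercise was meant to supply. The re-estimation lowered the evaluable target from 56 to 42, and 42 then leads to the 59 recruits in section 11.3 and to the power statement in the synopsis. What is at stake is the accuracy of that power statement. The type I error and the treatment estimate are not affected.

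**Working it through.** **Inputs.** From section 11.3: 34 interim patients in arms of 15 and 19; 42 evaluable for 80% power; 55 evaluable for 90%. From section 11.5.1: two-sided 0.05. From section 6.2.1: 1:1 allocation. The interim standard deviations and correlation are not printed and Figure 1 is not shown, so 42 cannot be reproduced directly. I work back from it.

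**1. The plan's own figures.** With a two-sample noncentral t calculation, 80% power at 42 in total implies a standardised effect d = 0.886 (0.865 by the normal formula). Keeping d = 0.886, 90% power needs 55.5, so 56 patients, against the stated 55. Conversely, 90% at 55 implies d = 0.890. The two stated targets agree with each other.

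**2. Variance lost by centring.** The expected within-arm sums of squares are 14σ² and 18σ², 32σ² in all. Drawing with replacement from the 34 centred values uses divisor 34:

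- expected variance = 32/34 × σ² = 0.941 σ²
- factor that restores the SD = sqrt(34/32) = 1.031

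The covariance of pain and morphine shrinks by the same 32/34, so their correlation is not distorted by this step.

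**3. Power with the variance restored,** if 42 and 55 gave exactly 80% and 90% without correction:

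| Target | Implied d | d × sqrt(32/34) | Power at that N | N for the nominal power |
|---|---|---|---|---|
| 42, 80% | 0.886 | 0.860 | 77.6% | 44.5 |
| 55, 90% | 0.890 | 0.864 | 88.2% | 58.3 |

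The shortcut 42 × 34/32 = 44.6 agrees. In whole patients, 80% needs 45, or 46 with equal arms. Section 11.3 counts 34 as recruited. If only 30 contributed values (assumption), the power at 42 is 77.2% and N is 42 × 30/28 = 45.0.

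**4. Check on a score like the one planned.** The protocol cites the SIA score without giving its formula, so any simulation rests on an assumed form (here a sum of ranks of pain and morphine) and on assumed SDs.

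- In four settings at 21 per arm (normal or skewed morphine, several assumed SDs), the sqrt(34/32) factor alone lowered the estimated power by 1.7 to 2.0 points.
- In a further setting (pain SD 1.91 and correlation 0.22 as in section 11.2, morphine SD 3.45 assumed), the described procedure reported 81.3% on average, the rescaled one 79.3%, against a true 76.8%.

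These runs support the direction and rough size. Their absolute power levels are not properties of this trial.

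**5. Sampling error, for scale.** A variance on 32 degrees of freedom has a 95% interval of 0.65 to 1.75 times its estimate. Applied to 42, that is about 27 to 73 patients. The chance that the uncorrected variance falls below the true one is P(χ² on 32 df < 34) = 63%, so in 37% of interim samples it errs the other way.

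**The case against.** The strongest reply is that the absence of a correction is inferred from silence. Section 11.3 is a narrative, the protocol defers detailed methodology to a separate analysis plan, and a scaling factor in simulation code is easily left out of a text. This stands as a limit on the point, and the fix allows for it. It does not remove the point: the section sets out pairing, centring, replacement and the effect ratio one by one, and the procedure so described is biased.

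A reader might also infer that the trial has less power than it states. The documents do not support that. The bias is an average over possible interim samples. Only one was drawn, its variance may have come out too high, and a shift of about 2 points is small beside the range of 27 to 73 patients. Sampling error is, however, mainly two-sided, whereas this bias has a known direction and an exact correction.

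Nor is there a sizeable general penalty merely for using one small sample. With an unbiased variance on 32 degrees of freedom, the average estimated power is about 80.4% against a true 80%. Larger gaps in simulation depend on the assumed score and SDs.

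Finally, there may be offsets. The primary model adjusts for duration of surgery and number of trocars, which the resampling as described does not. If these explained about 6% of the residual variance (assumption), 42 would again give 80%. The synopsis's 25% drop-out applied to 59 gives 44.25 evaluable, about 79.5% power at 44 after the correction. Section 11.3 itself uses 30%, which gives 59 × 0.70 = 41.3. Such offsets are speculative and do not repair the stated calculation.

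**Conclusion.** The point holds in a limited form. The procedure as described understates the within-arm variance by 32/34 on average, so the targets of 42 and 55 are mildly optimistic in expectation: about 78% and 88% power instead of 80% and 90%, or about 45 evaluable patients for 80%. This rests on three assumptions: no correction was made, 42 and 55 gave exactly the nominal power under the uncorrected procedure, and a two-sample t calculation approximates the SIA analysis. It is a small, correctable inaccuracy in a stated figure. It is not evidence that the trial is underpowered, and it is no argument against centring.

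**What to change.** Multiply the centred pain and morphine values by sqrt(34/32) = 1.031, or each arm by sqrt(n/(n-1)), which is 1.035 for 15 patients and 1.027 for 19. Use the number of patients who actually contributed values if it is below 34. Re-run Figure 1 and restate in section 11.3 and the synopsis the power that 42 and 55 evaluable patients give. Label any simulated figure with the score form and SDs behind it. If a correction was already in the code, one sentence in section 11.3 saying so is enough.

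The cost is one line of code and a slightly less favourable stated power. Recruitment does not need to change.
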